Appendix B: mHealth PP Usability Questionnaire (MAUQ)

University of Pittsburgh

School of Health and Rehabilitation Sciences
Department of Health Information Management

[name]
[name]
[contact]
[contact]
HIM: <http://www.shrs.pitt.edu/him>
SHRS: <http://www.shrs.pitt.edu>

mHealth App Usability Questionnaire (MAUQ) for Standalone mHealth Apps Used by Healthcare Providers

#	Statements	N/A	1	2	3	4	5	6	7
1.	The app was easy to use.		DISAGREE						AGREE
2.	It was easy for me to learn to use the app.		DISAGREE						AGREE
3.	The navigation was consistent when moving between screens.		DISAGREE						AGREE
4.	The interface of the app allowed me to use all the functions (such as entering information, responding to reminders, viewing information) offered by the app.		DISAGREE						AGREE
5.	Whenever I made a mistake using the app, I could recover easily and quickly.		DISAGREE						AGREE
6.	I like the interface of the app.		DISAGREE						AGREE
7.	The information in the app was well organized, so I could easily find the information I needed.		DISAGREE						AGREE
8.	The app adequately acknowledged and provided information to let me know the progress of my action.		DISAGREE						AGREE
9.	I feel comfortable using this app in social settings.		DISAGREE						AGREE
10.	The amount of time involved in using this app has been fitting for me.		DISAGREE						AGREE
11.	I would use this app again.		DISAGREE						AGREE
12.	Overall, I am satisfied with this app.		DISAGREE						AGREE
13.	The app would be useful for my healthcare practice.		DISAGREE						AGREE

14.	The app improved my access to delivering healthcare services.		DISAGREE         AGREE
15.	The app helped me manage my patients' health effectively.		DISAGREE         AGREE
16.	This app has all the functions and capabilities I expected it to have.		DISAGREE         AGREE
17.	I could use the app even when the Internet connection was poor or not available.		DISAGREE         AGREE
18.	This mHealth app provides an acceptable way to deliver healthcare services, such as accessing educational materials, tracking my own activities, and performing self-assessment.		DISAGREE         AGREE

In this questionnaire, 1 - strongly disagree, 2 – disagree, 3 – somewhat disagree, 4 – neither agree nor disagree, 5 – somewhat agree, 6 – agree, 7 – strongly agree

To determine the usability of an app, calculate the total and determine the average of the responses to all statements. The higher the overall average, the higher the usability of the app.

Please cite: Zhou L, Bao J, Setiawan A, Saptono A, Parmanto B, (2019), "The mHealth App Usability Questionnaire (MAUQ): Development and Validation Study", *JMIR mHealth and uHealth*, 7(4):e11500. DOI: 10.2196/11500. PMID: 30973342

Appendix C: Patient experience questionnaire

Questionnaire

Patient experience with wireless vital sign monitoring (WARD)

Date: _____ Patient ID: _____

Please answer every statement

How many days have the system been used: _____

Where did you have patch(es)/device(s) on you:

- Upper chest
- Shoulder
- Around your arm
- Under armpit
- Lower stomach
- Wrist

This section is about the patches/devices that were used for this specific study

I did not mind wearing the patches/devices while being in the hospital:

- Strongly agree

Questionnaire

Patient experience with wireless vital sign monitoring (WARD)

agree

neither agree nor disagree

disagree

strongly disagree

The patches/devices restrained my movements:

Strongly agree

agree

neither agree nor disagree

disagree

strongly disagree

The patches/devices disturbed my sleep at night:

Strongly agree

agree

neither agree nor disagree

disagree

strongly disagree

Questionnaire

Patient experience with wireless vital sign monitoring (WARD)

My experience with the patches/devices were overall good:

- Strongly agree
- agree
- neither agree nor disagree
- disagree
- strongly disagree

This section is about the methods of continuously monitoring patients and how this feel. In this section we will ask you to think less about the patches/devices and more about the monitoring as a concept

Being monitored continuously made me feel safe:

- Strongly agree
- agree
- neither agree nor disagree
- disagree
- strongly disagree

Questionnaire

Patient experience with wireless vital sign monitoring (WARD)

I was happy to know that the nurse would be notified if my condition worsened:

- Strongly agree
- agree
- neither agree nor disagree
- disagree
- strongly disagree

I felt left alone because the nurse did not measure my vital signs manually:

- Strongly agree
- agree
- neither agree nor disagree
- disagree
- strongly disagree

I think the continuous monitoring resulted in less contact with the nurses:

- Strongly agree
- agree

Questionnaire

Patient experience with wireless vital sign monitoring (WARD)

neither agree nor disagree

disagree

strongly disagree

The continuous monitoring gave me more privacy:

Strongly agree

agree

neither agree nor disagree

disagree

strongly disagree

Additional thoughts about your experience:

THANK YOU FOR YOUR PARTICIPATION

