Study procedure	
The study comprises two work packages:
 
Work package 1 (Monitoring for episodes of new onset AF):
 
Over 48-month, period patients with one of the above acute conditions will have vital signs monitored continuously for seven days during their hospital stay using a remote wireless monitoring system (Isansys Lifecare Ltd, Patient Status Engine). Where deemed clinically indicated, routine standard vital signs via stationary monitors will be continued. Surplus blood samples will be collected at the beginning of the monitoring period and then in line with routine blood sampling as clinically indicated. When clinically indicated, extra blood samples will be collected for cardiac biomarkers. Echocardiography will be performed by qualified sonographers where clinically indicated. Data collection will include demographics, routine blood results, diagnoses, past medical history, drug history, interventions, length of hospital stay, anaesthetic risk profiles, quality of life, clinical symptoms.
 
Work package 2 (Assessment of acceptability of and experience with a remote wireless monitoring system connected to an app by patients and health care professionals)
 
Patients in Work Package 2 will be asked to complete a questionnaire to explore their experiences with a remote wireless monitoring system. Health care professionals will participate in semi-structured interviews and complete the mHealth App Usability Questionnaire (MAUQ) for Standalone mHealth Apps Used by Healthcare Providers a standard questionnaire designed by the University of Pittsburgh.

Statistical Methodology and Analysis	
Descriptive statistics (mean, median, frequency of occurrences) will be used to summarise the data, univariable and multivariable analysis will be conducted for comparisons between groups, cluster analysis, generalised linear mixed effects models and survival analysis will be used (see statistical analysis plan). A two-sided p-value of <0.05 will be considered clinically significant.
 
Data will be used further for the application and development of machine learning algorithms, aiming at developing and establishing dynamic clinical decision support tools and virtual twins.

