(https://www.bma.org.uk/media/4z113khg/mental-capacity-act-england-and-wales.pdf?_ga=1*146j826*_up*MQ..*_ga*NDAXMDc0MTE1LjE3MTg4MzA1OTU.*_ga_F8G3Q36DDR*MTCxODgzMDU5NC4xLjAuMTcxODgzMDU5NC4wLjAuMA..). Therefore, for this study, different

approaches of obtaining consent, depending on the mental situation of a patient, need to be applied. This tiered approach will be applied independent from the care setting by trained research staff. Where applicable, will use the CAM-ICU tool to assess mental capacity.

We aim to recruit patients before they undergo either elective or emergency surgery or as soon as possible after admission with an acute condition as listed above. When elective surgery is planned, we

will approach patients before their surgery, i. e. either during their outpatient visit, following their outpatient visitor on the day of admission to hospital. At this point, we will inform them about the purpose of the study via the participant information sheet, and through explaining the study procedures and the associated risks and potential benefits. We will also explain that they will continue to receive standard routine care in addition to wCVSM. Patients can be informed about the study via telephone, email, or face to face, and depending on patient preferences further discussions will take place via phone or in person.

In situations requiring urgent or emergency interventions and when patients lack capacity due to the nature of their illness, a personal or legal representative will be consulted before or after the intervention, but before any study interventions are performed. This process is described in more detail below. For patients with acute medical conditions a similar approach will be taken.

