- Data and/or blood samples obtained so far can be used for the research purposes, but no further samples or data will be collected.
- On patient request all data obtained so far will be deleted from the research database in REDCap and all paper documents containing patient data obtained as part of the study will be destroyed. All blood samples obtained will be destroyed.
- The above options will be available on the retrospective consent form.

For patients who were unable to consent for themselves when enrolled in the study, retrospective consent will be sought in written form for them to remain in the study, once they regain capacity (retrospective consent).

Monitoring

Alongside standard care, vital signs will be monitored continuously for seven days after recruitment using the Isansys Lifecare Patient Status Engine (PSE), a CE-marked class 2a medical device, with wireless wearable biosensors recording single-lead continuous ECG, heart rate, heart rate variability, respiratory rate, temperature, oxygen saturation and non-invasive blood pressure, which are displayed on a tablet (Patient Gateway) in real time and securely stored on a server. Alerts can be sent directly to healthcare professionals using authorized mobile devices.

Alternative systems, e. g. Smartcardia platform (SCaAI patch and cloud platform, a CE Class IIa approved system with monitoring of 7-lead ECG, respiration, SpO₂, activity and cloud-based arrhythmia detection, may be used.

Blood sampling

Surplus serum blood samples will be collected on the day of recruitment (day 1), until day7 and within 24h before hospital discharge. Where a blood sample has been requested for clinical reasons, a serum blood sample will be added to the request if not yet included. Pseudonymized samples will be centrifuged, plasma or serum will be aliquoted, frozen and stored at -80°C for subsequent analysis. Serum samples will be transferred to the Liverpool Biobank at regular intervals to be available for future research. Serum samples will be used to determine cardiac biomarkers, including but not limited to troponins and natriuretic peptides and inflammatory markers, including but not limited to cytokines and interleukins. Samples of patients who decline use in future research will remain stored at freezers within the Liverpool University Hospitals NHS Foundation Trust and destroyed after this project has finished. A detailed flow diagram of blood sampling is provided in Appendix I.

Biomarker testing

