Appendix E. Study procedures

	Screening / Pre-study	1	2	3	Day 3-7	Discharge	Day 90
Inclusion and Exclusion criteria	X						
Medical history (preexisting condition, premedication)	X						
Consent	X						
Demographic data	X						
Admission diagnosis, Category of admission (elective, emergency)		X					
Surgical parameters (type & duration of procedure, intraoperative transfusion)		X					
APACHE II		X					
SOFA Score		X	X	X			
Standard vital signs (SBP, DBP, MAP, HR, RR, SpO2, if indicated CVP, CO)	X	X	X	X			
Continuous Vital Signs monitoring		X	X	X	X		
Laboratory parameters (if clinically indicated)		X	X	X	X	X	
Collection of surplus routine blood samples (when available)	X	X	X	X	X	X	
Transthoracic Echocardiography (if clinically indicated and available)	X	X	X	X			
Vasopressor and inotrope use	X	X	X	X	X		
Documented episodes of AF (in clinical notes and on wCVSM)		X	X	X	X	X	X
Concomitant cardiac Medication (antiarrhythmics, diuretics, statins, antihypertensives)	X	X	X	X	X	X	X
Mortality						X	X
EQ-5D-5L						x	x
Duration of organ support (Begin and end of RRT, mechanical ventilation, oxygen therapy)	X	X	X	X	X	X	X
Length of stay (ICU, Hospital)					X	X	X
Cardiac Recovery							X
Cardiac diagnoses / complications (episodes of AF; congestive heart failure, thromboembolic event, stroke)	X	X	X	X	X	X	X
Non-cardiac diagnoses / complications (sepsis, pneumonia, wound infection, anastomotic leak, bleeds)		X	X	X	X	X	X

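### One Appendix C statement assumes that nurses took no manual measurements, so answers from patients who were still measured manually cannot be interpreted

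*Protocol*

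**What the plan says.** Appendix C holds nine agree/disagree statements, each with five response options from strong agreement to strong disagreement and a neutral midpoint. The respondent is told: "Please answer every statement". One statement, in the part about monitoring as a concept, reads "I felt left alone because the nurse did not measure my vital signs manually". No 'not applicable' option is printed. The only background questions are how many days the system was used and where the patches or devices were worn.

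Two procedural sections describe the device as an addition to usual care. Consent and Enrolment Procedures says of the discussion with patients: "We will also explain that they will continue to receive standard routine care in addition to wCVSM". The Monitoring section under Study procedures says: "Alongside standard care, vital signs will be monitored continuously for seven days after recruitment". The Introduction's section on wireless monitoring describes manual measurement as part of nurses' existing routine.

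Two other places are less definite. The synopsis says: "Where deemed clinically indicated, routine standard vital signs via stationary monitors will be continued". Appendix E marks standard vital signs at screening and on days 1, 2 and 3. It leaves that row blank in the Day 3-7 column, where continuous monitoring is marked.

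Patient acceptability is a secondary objective and a listed outcome of work package 2, where it is to be assessed semi-quantitatively. The synopsis puts 25 patients in that work package.

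**The concern.** The statement joins a feeling (being left alone) to a fact taken as given (no manual measurement by the nurse). If the fact is untrue for a patient, the rating no longer measures the feeling. That patient's natural responses are to disagree, because the event did not happen, or to choose the midpoint. Neither shows how the patient would feel without manual observations.

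This is the only statement that asks directly about the loss of manual measurement. The Introduction expects wireless monitoring to change the nurses' measurement routine, and work package 2 is meant to produce an implementation guide and to share its results with the WARD24/7 international team. A favourable tally on this item could be cited as evidence that patients accept a change that some of them, perhaps most, did not experience.

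**Working it through.** The protocol attaches no figure or calculation to this item, so there is nothing to reproduce. The check is a comparison of the text, followed by an illustration of scale.

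**Does the premise fit the procedures?**
- Consent and Enrolment Procedures and Monitoring: usual care continues and the device is added. With manual measurement described as routine nursing work, the premise would be false for a patient receiving that care.
- Synopsis: continuation depends on clinical indication and refers to stationary monitors. The premise could be true for some patients.
- Appendix E: standard vital signs are marked up to day 3 and unmarked for Day 3-7. The row does not say who measures or by what means. The premise could be true on some days.

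The 25 patients may therefore be a mixture. Nothing recorded in Appendix C separates those for whom the premise was true from the rest.

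**Can a patient for whom it is false decline to answer?** Not within the form: every statement is to be answered and no 'not applicable' box exists. The staff questionnaire in Appendix B does have an N/A column.

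**How large could the effect be?** Appendix C has no total, mean or threshold; the averaging instruction in Appendix B belongs to the staff questionnaire. The figures below are therefore assumptions.

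*Assumption A: a nine-item mean, each item coded 1-5 with 5 favourable.* Let f be the share of patients still measured manually, s the score they give this item, and b the score they would otherwise have given. The shift in the mean is f × (s − b) / 9. With b = 3:

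| f | s = 3 (midpoint) | s = 4 | s = 5 |
|---|---|---|---|
| 0.5 | 0 | 0.5 × 1/9 = 0.06 | 0.5 × 2/9 = 0.11 |
| 1 | 0 | 1/9 = 0.11 | 2/9 = 0.22 |

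*Assumption B: the item reported alone as the percentage disagreeing.* Let q be the share disagreeing among patients not measured manually, and suppose everyone still measured manually disagrees. The reported share is f + (1 − f) × q.
- f = 0.5, q = 0.5: 0.5 + 0.5 × 0.5 = 75%
- f = 0.5, q = 0.7: 0.5 + 0.5 × 0.7 = 85%
- f = 1: 100%, whatever q is

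Under B the distortion can be sizeable for this one item. Under A it is small, and it is zero if these patients use the midpoint.

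**The case against.** The strongest reply is that the premise is not shown to be false for everyone. The synopsis makes continuation conditional, Appendix E leaves Day 3-7 blank, and usual care does not fix how often a nurse measures by hand. This stands. A reader might infer that no patient experienced the loss of manual measurement; the documents do not establish that.

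A reader might also infer that disagreement is forced and that overall acceptability is inflated. Neither is supported. The midpoint is available, no scoring rule exists, and the net direction over nine statements is unknown: continued nurse visits could, for instance, lower agreement with the statement on privacy.

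It is tempting as well to add the neighbouring statement, "I think the continuous monitoring resulted in less contact with the nurses". It should not be added. It carries no assumed fact, asks about a perceived effect, and can be answered validly whether or not manual rounds continued. If contact did not fall, disagreement is simply correct.

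Finally, this is one item in an exploratory questionnaire with a free-text field, no hypothesis test and no bearing on the primary outcome. That limits its weight. It does not make the item interpretable, and the uncertainty about who was still measured manually is itself a reason to record it.

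**Conclusion.** The point holds for one of the nine statements. It takes the absence of manual measurement as given, must be answered, and offers no way to mark it as not applying, while two procedural sections say usual care continues. Answers from patients still measured manually cannot be read as acceptance of losing manual observations. If their disagreement is tallied as favourable, acceptability may be biased upward.

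The size is unknown and could be zero. It depends on the share of the 25 patients still measured manually, on how they use the scale, and on a scoring method that Appendix C does not state. This is a modest, cheaply corrected weakness in a secondary outcome.

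**What to change.** - In Appendix C, add one question asking whether nurses still measured vital signs manually while the system was worn, or put a 'not applicable' box on this item.
- Report the item by that answer and keep non-applicable responses out of any acceptability summary.
- State that, where manual observations continued, acceptability refers to monitoring added to standard care.
- Reconcile the synopsis, Consent and Enrolment Procedures, Monitoring, Appendix C and Appendix E on whether, and for how long, manual measurement continues. Which arrangement applies is for the investigators to state.
- Leave the statement about contact with nurses unchanged.

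The cost is one extra question for 25 patients and a sentence on reporting. There is a small downside: slightly less direct comparability with WARD partner data on this item.

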Appendix D. Timeline of study activities

[figure not shown]

Figure 1. Provisional WARD-UK/PULSE-GI study timeline

Appendix E. Study procedures

	Screening / Pre-study	1	2	3	Day 3-7	Discharge	Day 90
Inclusion and Exclusion criteria	X						
Medical history (preexisting condition, premedication)	X						
Consent	X						
Demographic data	X						
Admission diagnosis, Category of admission (elective, emergency)		X					
Surgical parameters (type & duration of procedure, intraoperative transfusion)		X					
APACHE II		X					
SOFA Score		X	X	X			
Standard vital signs (SBP, DBP, MAP, HR, RR, SpO2, if indicated CVP, CO)	X	X	X	X			
Continuous Vital Signs monitoring		X	X	X	X		
Laboratory parameters (if clinically indicated)		X	X	X	X	X	
Collection of surplus routine blood samples (when available)	X	X	X	X	X	X	
Transthoracic Echocardiography (if clinically indicated and available)	X	X	X	X			
Vasopressor and inotrope use	X	X	X	X	X		
Documented episodes of AF (in clinical notes and on wCVSM)		X	X	X	X	X	X
Concomitant cardiac Medication (antiarrhythmics, diuretics, statins, antihypertensives)	X	X	X	X	X	X	X
Mortality						X	X
EQ-5D-5L						x	x
Duration of organ support (Begin and end of RRT, mechanical ventilation, oxygen therapy)	X	X	X	X	X	X	X
Length of stay (ICU, Hospital)					X	X	X
Cardiac Recovery							X
Cardiac diagnoses / complications (episodes of AF; congestive heart failure, thromboembolic event, stroke)	X	X	X	X	X	X	X
Non-cardiac diagnoses / complications (sepsis, pneumonia, wound infection, anastomotic leak, bleeds)		X	X	X	X	X	X

Appendix F. Scores

SOFA-Score

SOFA Score	0	1	2	3	4
Respiration PaO ₂ /FiO ₂	>400	<400	<300	<200	<100
Platelet count (10 ³ /μl)	>150	<150	<100	<50	<20
Bilirubin (mg/dl)	<1.2	1.2-1.9	2.0-5.9	6.0-11.9	>12
Cardiovascular	No hypotension	MAP <70 mmHg	Dobutamine (any dose)	Norepinephrine/epinephrine ≤0.1μg/kg/min	Norepinephrine/epinephrine >0.1μg/kg/min
GCS	15	13-14	10-12	6-9	<6
Creatinine (mg/dl) or UO (ml/d)	<1.2	1.2-1.9	2.0-3.4	3.5-4.9 ≤500	>5.0 <200

ASA-Score

ASA I	Normal healthy patients
ASA II	Patients with mild systemic disease
ASA III	Patients with severe systemic disease that is limiting but not incapacitating
ASA IV	Patients with incapacitating disease which is a constant threat to life
ASA V	Moribund patients not expected to live more than 24 hours
ASA VI	A declared brain-dead patient whose organs are being removed for donor purposes

APACHE-Score

Points	+4	+3	+2	+1	0	+1	+2	+3	+4
Temp. °C	≥41	39-40.9		38.5-38.9	36-38.4	34-35.9	32-33.9	30-31.9	≤29.9
MAP (mmHg)	≥160	130-159	110-129		70-109		50-69		≤49
HF/min	≥180	140-179	110-139		70-109		55-69	40-54	≤39
AF/min* ¹	≥50	35-49		25-34	12-24	10-11	6-9		≤5
Oxygenation	≥500	350-499	200-349		71-199	61-70		55-60	<55
pH	≥7.7	7.6-7.69		7.5-7.59	7.33-7.49		7.25-7.32	7.15-7.24	<7.15
Na ⁺ (mmol/L)	≥180	160-179	155-159	150-154	130-149		120-129	111-119	≤110
K ⁺ (mmol/L)	≥7	6.6-6.69		5.5-5.59	3.5-5.4	1.0-3.4	2.5-2.9		≤2.5
Creatinine (mg/dl) * ²	≥3.5	2.0-3.4	1.5-1.9		0.6-1.4		<0.6		
Hematocrit (%)	≥60		50-59.9	46-49.9	30-45.9		20-29.9		<20
Leukocytes (x1000)	≥40		20-39.9	15-19.9	3-14.9		1-2.9		<1
GCS	Points= 15-current GCS								

*1 spontaneous breathing or mechanical ventilation

*2 AKI receives double points

